## 6.4 Statistical Methods

### 6.4.1 Baseline Data

Descriptive statistics for demographic, behavioral, and environmental characteristics measured at baseline will be examined across the two treatment groups to assess the success of the randomization.

### 6.4.2 Analysis of Primary Outcomes of Interest

#### 6.4.2.1 *Specific Aim 1*

##### Primary outcomes

In order to determine the effectiveness of the Opening Doors to Early Intervention Program on child developmental status, our primary outcome for this aim is the Bayley-III cognitive subscale measured at 12 months follow-up. For our primary outcome, a linear mixed effects approach will be used to model differences in cognitive functioning between intervention groups accounting for clustering due to practice. Such an approach is advantageous for offering flexible means for accounting for potential issues that arise in randomized trials. For example, baseline patient characteristics that were not balanced across intervention groups by the randomization process can be accounted for through covariate level adjustment. Also, differential drop-out and loss to follow-up between groups can be accounted for by incorporating missing data methods such as multiple imputation.

##### Secondary outcomes

Secondary outcomes include the Bayley-III language, motor, and socioemotional subscales and the binary outcomes of whether patients complete EI referrals and services at 12 months. Descriptive statistics for demographic, behavioral, and environmental characteristics measured at baseline will be examined across the two treatment groups to assess the success of the randomization. The secondary outcomes can be modeled using either a linear or logistics mixed effects model, which has similar flexibility. As a secondary analysis, we will examine differences in dosage (duration of EI service use and number of EI service visits) between intervention groups among those eligible for services. We will also examine the impact of public policy changes on the proportion eligible for EI and on the number of service visits pre- and post-change. In addition, we will examine the effects of the intervention by race/ethnicity group, sex, and age group (<18 months, >18 months) to assess for differential intervention effects.

---

#### ***6.4.2.2 Specific Aim 2***

We will assess whether family engagement is a mediator of intervention treatment effects. We will address this aim by focusing on the role of family engagement using the EI Engagement questionnaire at 3, 6, 9, and 12 months as a mediator of the effect of the intervention on the study outcomes. Family engagement will occur post randomization and thus can be considered as a potential mediator as opposed to being a confounder. The response models discussed previously will be modified to include the EI Engagement questionnaire overall and domain scores as potential mediators in separate models to evaluate its mediating role in the association of interest. The association between outcome measures and the intervention conditional on the covariate will be compared to the marginal association estimated by the first aim.

#### ***6.4.2.3 Specific Aim 3***

We will evaluate whether literacy, the home learning environment, adverse childhood experiences and poverty moderate treatment effects on pre-specified outcomes. To do so, the previously described models will be modified to include interaction terms between the intervention group assignment and each of these potential effect modifiers in addition to a main effect for the given variable. This model will then be used to test whether the association between intervention and the outcome differs by the given covariate. Factors of importance from the background section that will be used in this aim include family level variables (race/ethnicity, maternal education level, family income category, StimQ total scores, and SAHL scores).

#### ***6.4.2.4 Specific Aim 4***

By way of the COVID-19 Rapid Response sub-study, we will determine changes in use of and need for safety net programs among low-income families of children with developmental disabilities during the current COVID-19 pandemic in Philadelphia.

#### ***6.4.2.5 Specific Aim 5***

By way of the Trauma-Informed Co-parenting Sub-study, we will adapt an evidence-based co-parenting program for use among caregivers who have experienced significant trauma and chronic stress as a child. We will use qualitative methods to modify the FF program into a trauma-informed primary care-based co-parenting intervention for use among caregivers with traditional or non-traditional family structures who have been exposed to trauma and chronic stress as children.

### **6.5 Sample Size, Statistical Power and Analysis Plan**

Our target sample size accounting for clustering by practice site for patients with complete 12-month follow-up is 300 participants. Assuming at least an 80% follow-up rate, the number needed to recruit to obtain this final sample size is about 360. Since a partial goal of the proposed intervention is to increase patient engagement, the rate of drop out is likely to be lower among the intervention group. If we conservatively assume that the drop-out rate among control patients is double that of patients on the intervention, the sample of patients

with complete follow-up will consist of approximately 130 control patients and 170 intervention patients.

Using the Bayley-III cognitive subscale as a primary outcome, we assert that the proposed intervention would be successful if it resulted in an increase of 3 points or more on this subscale. This is the minimal clinically significant outcome difference. Thus, based on the proposed sample size, we would obtain 96% power to detect a clinically meaningful difference in the Bayley-III cognitive scores. The power was estimated based on a simulation study that assumed that the sole impact of the intervention was on increasing enrollment into EI. Based on expected cognitive improvements due to EI found by Guralnick et al, we further assume that children who enrolled in EI had an average increase over a 12 month period of 10 points on the cognitive scale with a standard deviation of 1 point compared to patients who did not enroll. Based on these assumptions, an increase of 3 points on the cognitive scale between the intervention and control group would be the result of an increased rate of enrollment from 50% among controls to 80% among the intervention group. These rates of enrollment are consistent with rates suggested by our pilot data (Preliminary Studies Section).

**Figure 1** *Assessment of power to detect a clinically meaningful difference*

Power	n	
0.96	300	Assuming a minimal clinically significant outcome difference ( $\geq 3$ points increase in the BSID-III cognitive subscale)

If this level of mediation by engagement and enrollment rates is replicated in the proposed trial, such differences should be adequately characterized by the proposed mediation analysis. To assess power to detect moderating effects, we use dichotomized literacy as an example based on having a SAHL score  $\leq 14$ . We assume a rate of inadequate literacy of 50% in each group and that the overall effect of the intervention on the cognitive score is the same as before. Using a simulation study based on these assumptions, the proposed sample size would give us approximately 84% power to a 6-point difference in differences for the effect of the intervention among children whose parents have inadequate literacy compared to children whose parents have adequate literacy.

**Figure 2** *Assessment of power to detect moderating effects*

Power	n	
0.84	300	Assuming a rate of inadequate literacy of 50% in each group and that the overall effect of the intervention on the cognitive score is the same as before.

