## **3.2 Allocation to Treatment Groups and Blinding**

In this study, 360 eligible children will be randomized 1:1 to the FN or usual care consisting of routine Child Find procedures. We chose a randomized design, because it is most effective at guarding against bias and will ensure that patients in both arms are similar in observed and unobserved characteristics. The initial randomization will be stratified by practice site, child sex, and age group (0-<18 months old and 18-30 months old) to ensure

balance between groups. We will control post-hoc statistically for any imbalances that arise. Allocation concealment (blinding of the treatment assignment) will be implemented using sealed, opaque envelopes, along with stratification, and randomly permuted blocks of unequal sizes (to prevent providers and patients from manipulating the randomization). Treatment assignment will be done at the time of enrollment following informed consent and patients will be followed over time with measures related to EI referral completion, EI services completion, and patient engagement collected at baseline, 3, 6, 9, and 12 months as well as child developmental status around 12 months.

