#### **3.3.2 Total Number of Study Sites/Total Number of Subjects Projected**

A total of 410 subjects are anticipated between the two subject groups designated for this study. The first group of subjects will include 360 participants for the Main RCT study, and these subjects will be recruited for the COVID-19 sub-study and also for Phase 2 of the Trauma-Informed Co-parenting Sub-study. The second group of subjects (Delphi Consensus group) will include up to 50 experts that will participate in Phase 1 of the Trauma-Informed Co-parenting Sub-study. Additional descriptions for each study are provided below:

The Main RCT study will be conducted at approximately 4-6 CHOP primary care practices in Philadelphia. Recruitment will stop when approximately 360 subjects are enrolled. It is expected that approximately 360 subjects will be enrolled to produce 300 evaluable subjects.

The COVID-19 sub-study will recruit about 128 participants, one parent from each of the currently enrolled parent-child dyads from the Main RCT.

The Trauma-Informed Co-parenting Sub-study will recruit and enroll a total of around 50 parent participants from the Main RCT and up to 50 experts in childhood trauma.

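### Protocol 6.5: 130 control and 170 intervention completers imply roughly five-fold, not doubled, control dropout; and 360 enrolled at the 80% follow-up floor gives 288 evaluable, not 300

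*Protocol*

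**What the plan says.** Protocol section 6.5 makes three linked planning statements.

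- The target "for patients with complete 12-month follow-up is 300 participants".
- On how many children to enrol for that target, it states: "Assuming at least an 80% follow-up rate, the number needed to recruit to obtain this final sample size is about 360".
- On loss by arm, it begins: "If we conservatively assume that the drop-out rate among control patients is double that of patients on the intervention, the sample of patients". The same sentence then gives the resulting counts in each arm: "with complete follow-up will consist of approximately 130 control patients and 170 intervention patients".

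Section 3.2 fixes the starting point for each arm: "360 eligible children will be randomized 1:1 to the FN or usual care". Section 9.1.1 also gives 1:1 allocation. Section 3.3.2 repeats the overall pair of numbers: "It is expected that approximately 360 subjects will be enrolled to produce 300 evaluable subjects".

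The SAP gives no dropout rate, no evaluable number and no arm split, so these Protocol sections are the only source.

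**The concern.** The arm counts and the assumption said to produce them do not agree. Equal arms of 180 cannot lose children in a 2:1 ratio and finish at 130 and 170. The stated recruitment number also does not deliver its target at the stated minimum follow-up.

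This is the only place in the documents where expected loss is quantified by arm. Section 6.3 names dropout and loss to follow-up as the main source of bias after randomisation. Someone who later compares observed with planned attrition would find two incompatible plans: a gap between arms of 22.2 percentage points from the printed counts, or 11.1 points from the stated doubling with 300 completers.

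**Working it through.** **Inputs.** 360 randomised 1:1, so 180 per arm (3.2). Control dropout twice intervention dropout, with 130 and 170 completers (6.5). Follow-up of at least 80% and 300 completers (6.5). 360 enrolled for 300 evaluable (3.3.2).

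**1. Dropout implied by the printed counts.**

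- Control: (180 − 130)/180 = 50/180 = 27.8%.
- Intervention: (180 − 170)/180 = 10/180 = 5.6%.
- Ratio: 50/10 = 5.0.
- Total completers: 130 + 170 = 300, which matches the target. The error is in the split.

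**2. Can the printed split be reproduced under some reading of doubling?**

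- *Rounding to the nearest ten.* With 125–135 control and 165–175 intervention completers, the smallest ratio is (180 − 135)/(180 − 165) = 45/15 = 3.0 and the largest is 55/5 = 11.0. It never reaches 2.
- *Odds or hazard scale.* The printed counts give an odds ratio of (50/130)/(10/170) = 6.5 and a hazard ratio of ln(130/180)/ln(170/180) = 5.7. Imposing a ratio of 2 on either scale with 300 completers gives about 142/158 (odds) or 141/159 (hazard).
- *A base of 375 (187.5 per arm).* 57.5/17.5 = 3.3.
- *The base at which 130/170 would be a doubling.* n − 130 = 2(n − 170) gives n = 210 per arm. That is 420 randomised and 300/420 = 71% follow-up. Neither figure is in the Protocol.

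None of these yields 130/170 from the stated assumptions.

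**3. What a true doubling gives.** Let intervention dropout be x and control dropout 2x. Then 180(1 − x) + 180(1 − 2x) = total completers.

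| Scenario from 360 enrolled | Control dropout | Intervention dropout | Completers, control/intervention | Gap (points) |
|---|---|---|---|---|
| As printed | 27.8% | 5.6% | 130/170 | 22.2 |
| Doubling, 300 completers | 22.2% | 11.1% | 140/160 | 11.1 |
| Doubling, 288 completers | 26.7% | 13.3% | 132/156 | 13.3 |

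**4. Recruitment number.**

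- 0.80 × 360 = 288, which is 12 below 300 (12/300 = 4%).
- 300/0.80 = 375 to recruit at 80% follow-up.
- 300/360 = 83.3% follow-up needed from 360.
- 360 equals 300 × 1.2. Multiplying by 1 + d instead of dividing by 1 − d would produce it, though that cause is only an inference.

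**5. Effect on power.** The documents give no total outcome SD, alpha or sidedness. I assume two-sided 0.05, and an SD of 6.9 chosen because it returns about the stated 96%. Power = Φ(3/(SD × √(1/n_control + 1/n_intervention)) − 1.96).

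- 130/170: 96.2%
- 140/160: 96.4%
- 132/156: 95.7%

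The difference between 130/170 and 132/156 is 0.02, 0.5, 1.3 and 1.0 points at SDs of 5, 7, 10 and 15. Because the SD is back-solved, this shows only how sensitive power is to the split. It does not check the 96%.

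**The case against.** Several points on the other side stand.

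- **The 288 against 300 gap is a loose boundary, not a flat contradiction.** The follow-up rate is given as a minimum and the recruitment number as approximate, and 83.3% follow-up meets the minimum. Section 3.1.1 cites prior follow-up above 80%. It remains true that a number described as needed to reach a target should reach it at the stated floor.
- **Five-fold is not an exact figure.** Both arm counts are marked as approximate. Rounding allows anything from three-fold to eleven-fold, but not two-fold.
- **The misprint does not flatter the design.** For a fixed 300 completers, 130/170 is slightly less efficient than 140/160.

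Two stronger readings are tempting, and the documents support neither. A reader might infer that the power claim rests on the wrong split: "we would obtain 96% power to detect a clinically meaningful difference in the Bayley-III cognitive scores". But section 6.5 ties that figure to the proposed sample size, and its power table lists only n = 300. It does not say whether the simulation used 130/170, 150/150 or another split. A reader might also infer that the informative-dropout sensitivity analyses in section 6.3 are built on these rates. Section 6.3 names no rates and does not point to 6.5.

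**Conclusion.** The inconsistency is real and confined to the planning figures. The stated doubling and the printed 130/170 cannot both hold with 180 per arm. The counts imply about five-fold dropout, and at least three-fold after allowing for rounding. With 300 completers, the printed gap of 22.2 points is twice the 11.1 that the doubling implies; against the 13.3 points for 288 completers it is about 1.7 times (22.2/13.3). The evaluable number is a lesser fault, 4% short at the 80% floor.

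The arm-split result needs only the Protocol's own numbers and 1:1 allocation. The view that the power effect is negligible (half a point or less) rests on an assumed SD of 6.9, two-sided 0.05 and a simple two-sample normal formula, whereas the Protocol used simulation and plans a mixed model clustered by practice. Nothing here shows that the trial is underpowered, that the 96% was computed on the wrong split, or that the endpoint or primary analysis is affected.

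**What to change.** Restate sections 6.5 and 3.3.2 so that the follow-up rate, evaluable total, dropout ratio and arm counts agree. Either version works:

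- 80% follow-up: 360 enrolled, 288 evaluable, 132 control and 156 intervention under doubled control dropout; or
- 83.3% follow-up: 360 enrolled, 300 evaluable, 140 control and 160 intervention under doubled control dropout.

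In both cases drop 130/170, or keep it and label it as a roughly five-fold dropout scenario. It would also help to state which arm split the power simulation used, since 6.5 does not say.

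The cost is Protocol wording. Under the first version the evaluable number becomes slightly less favourable; the second commits the study to better follow-up than its stated floor. Enrolling 375 at 80% would also reconcile the totals, but it is a much larger change, and the small power effect gives no reason on its own to require it.

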## 1 BACKGROUND INFORMATION AND RATIONALE

### 1.1 Main RCT

Early childhood is a critical period in which young children attain developmental milestones necessary for cognitive, motor, language, and socio-emotional functioning. Unfortunately, developmental delays are commonly encountered among children under the age of 3 years. These delays occur when a child does not reach important milestones, e.g. independent ambulation, within an expected period of time in one or more domains. Twelve to sixteen percent of young children are estimated to have developmental delays or disorders.

Although developmental delays have been associated with a number of medical and genetic conditions, most are idiopathic and do not possess phenotypic characteristics that allow for easy recognition. As such, developmental delays when not identified early contribute to social and emotional problems and result in poor educational and functional outcomes. Lifetime costs for individuals with developmental disabilities has been estimated to exceed \$60 billion in 2003 U.S. dollars.

Identifying developmental delays and instituting early intervention (EI) services in a timely fashion are of critical importance to optimize child wellbeing. The EI Program (Part C of the Individuals with Disabilities Education Act) was established by Congress in 1986 to provide funding for states to establish and maintain programs of services to meet the needs of children with developmental delays and disabilities and their families. The evidence base for the effectiveness of EI services has been established. At-risk children without the benefit of early intervention services experience average declines in cognitive development of approximately 0.5-0.75 SD units. EI systems have been found to prevent or reduce cognitive declines in at-risk children in the first five years of life and to mitigate stressors among at-risk families that contribute to developmental delays. Reviews of EI programs found average improvements of 0.43-0.75 SD (~8-12 IQ points) in cognitive function. However, much of the research on the effectiveness of EI on at-risk children has involved premature infants, so it isn't clear how effective EI services are for term or late preterm at-risk children.

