### **3.4.1 Inclusion Criteria**

#### ***3.4.1.1 Main RCT***

- 1) Child is <30 months old at time of enrollment
- 2) Child was born >35 weeks estimated gestational age
- 3) Parent-child dyad reside in Philadelphia and present at a CHOP primary care practice located in Philadelphia
- 4) Parents are English or Spanish speaking
- 5) Child has recently been referred to the Philadelphia Infant Toddler Early Intervention Program in Philadelphia County

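### The 96% power in Protocol Section 6.5 does not follow from its printed inputs, and is hard to reconcile with the EI effect cited in Section 1.1 if that effect applies

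*Protocol*

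**What the plan says.** Protocol Section 6.5 targets 300 children with 12-month data, described as allowing for clustering by practice. It assumes at least 80% follow-up from about 360 recruited. It assumes that "the drop-out rate among control patients is double that of patients on the intervention" and arrives at about 130 control and 170 intervention completers. A 3-point gain is called the minimal clinically significant difference, and the text concludes that "we would obtain 96% power to detect a clinically meaningful difference in the Bayley-III cognitive scores".

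That figure comes from a simulation in which "the sole impact of the intervention was on increasing enrollment into EI". Enrolled children have "an average increase over a 12 month period of 10 points on the cognitive scale with a standard deviation of 1 point" relative to those not enrolled. The 3 points come from an "increased rate of enrollment from 50% among controls to 80% among the intervention group". Figure 1 repeats 0.96 at n = 300. Alpha, sidedness, the spread of Bayley scores between children, a site effect and the simulation model are not printed.

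Protocol Section 1.1 reports from reviews of EI programs "average improvements of 0.43-0.75 SD (~8-12 IQ points) in cognitive function". It cautions that "much of the research on the effectiveness of EI on at-risk children has involved premature infants". This trial requires "Child was born >35 weeks estimated gestational age".

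**The concern.** The only SD in the power statement is 1 point, and it is attached to the EI gain. Power for a difference in means depends on how far scores vary between children, and that quantity is missing. A reader cannot tell what produced 96%.

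Section 6.5 is the only quantitative support for 300 completers on the primary endpoint, and Section 1.3.1.1 describes the sample sizes as adequately powered. For 3 points at 130/170, power stays at 80% or more only if the total SD is about 9.2 or less, and it drops below 50% above about 13.1. Without a stated SD, nobody can judge beforehand whether a null result would count against a 3-point benefit.

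**Working it through.** **Inputs.** From Section 6.5: gain 10 with SD 1, enrolment 0.5 and 0.8, completers 130 and 170, difference 0.30 × 10 = 3. Assumed, because not printed: two-sided alpha 0.05 and a comparison of two means. Power = Φ(difference/SE − 1.960).

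**1. The plan's own figure.** Arm variance = 100p(1 − p) + p, reading SD 1 as the spread of the gain among enrollees.
- Control: 25 + 0.5 = 25.5 (SD 5.05). Intervention: 16 + 0.8 = 16.8 (SD 4.10).
- SE = √(25.5/130 + 16.8/170) = 0.543.
- Power = Φ(3/0.543 − 1.960) = 99.98%. A 20,000-run simulation gives 99.99%.
- Two-sided alpha of 0.10, 0.01 and 0.001 gives 99.99%, 99.8% and 98.7%. No usual alpha leads to 96%.

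**2. What 96% needs.** SE = 3/(1.960 + 1.751) = 0.808. With √(1/130 + 1/170) = 0.1165:
- total SD = 0.808/0.1165 = 6.9, which is an extra between-child SD of about 5.1 on top of the enrolment mixture; or
- design effect = (0.808/0.543)² = 2.2.

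At a total SD of 6.94, the 10-point gain is 10/6.94 = 1.44 SD. That is about twice the top of the Section 1.1 range (1.44/0.75 = 1.92).

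**3. Section 1.1's effect, if it applies.** SD = points/effect size; power is for exactly 3 points at 130/170.

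| Pairing | Implied SD | Power |
|---|---|---|
| 8/0.75 | 10.7 | 67% |
| 12/0.75 | 16.0 | 36% |
| 8/0.43 | 18.6 | 28% |
| 12/0.43 | 27.9 | 15% |

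Rows two and three pair like with like. The outer rows cover every possible pairing.

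Working in SD units avoids the point scale. A 30-percentage-point enrolment rise gives 0.30 × 0.43 = 0.129 SD to 0.30 × 0.75 = 0.225 SD, with power of 20% to 49%. This is power for that effect, not for 3 points.

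**4. Completers.**
- 360/2 = 180 per arm. 130/170 means dropout of 50/180 = 27.8% and 10/180 = 5.6%, a ratio of 5 rather than 2.
- 300/0.80 = 375, and 360 × 0.80 = 288. Getting 300 from 360 needs 83.3% follow-up.
- Double control dropout with 300 completers: 180(1 − 2d) + 180(1 − d) = 300 gives d = 11.1%, so 140/160.
- Double control dropout with 288 completers: d = 72/540 = 13.3%, so 132/156.

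The split hardly affects power: at SD 16 it is 36% (130/170), 37% (140/160) and 35% (132/156).

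**The case against.** **The simulation may be sound.** It may have used a residual SD or site effect that was not printed, and Section 6.5 does say clustering was allowed for. The SD of 1 might also describe something other than child-level spread, in which case the printed inputs give no power at all. This stands, and it limits the point to reproducibility. The stated 96% is lower than 99.98%, so it does not overstate its own printed inputs. Clustering is not an obvious source of a 2.2-fold variance increase, because children are randomised individually within practice strata (Sections 3.2 and 9.1.1).

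**Section 1.1 may not transfer.** Its figures are approximate IQ points from reviews, largely of premature infants, and the pairing of points with SDs is not given. Only one of the two reviews it cites for this effect is also cited in Section 6.5. This stands too. A reader might infer that the protocol contradicts itself, or that true power is 28-36%. The documents support neither: both need an SD that no document states. What survives is that no pairing brings power for 3 points above 67%.

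**Covariate adjustment could shrink the SD.** Sections 6.3 and 6.4.2.1 allow it, and Section 5.1.1 takes developmental assessments from the medical record. But Table 1 schedules the BSID-III only at 12 months, and going from SD 16 to 6.94 requires 1 − (6.94/16)² = 81% of variance explained.

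**Conclusion.** The point holds as a power figure that cannot be reproduced: 96% is stated, while the printed inputs give about 99.98% at an assumed two-sided 0.05. Something unprinted, equivalent to a total SD of about 6.9 or a design effect of about 2.2, must account for the gap. It is tempting to conclude that the simulation was run wrongly. That is not shown.

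The figure is also hard to reconcile with the EI effect in Section 1.1. This second part depends on assuming that effect applies here, with power for 3 points then 36-28% like-for-like and 67-15% over all pairings. The completer inconsistencies are firm arithmetic, but they have little influence on power.

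**What to change.** In Section 6.5 and Figure 1:
- State alpha and sidedness, score scale, total outcome SD with its source, site effect and simulation model.
- Name the analysis being powered. Section 6.4.2.1 specifies a linear mixed model, while the SAP (Aim 1, Hypothesis 1c) specifies logistic regression for the cognitive and language scores. Settle this first, then rerun the simulation.
- Replace the single 96% with power, and the difference detectable at 80% power (2.802 × SE), over a labelled SD range. An example, with SDs derived from Section 1.1 as a stated assumption:

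| Total SD | Power for 3 points, 140/160 | Power for 3 points, 132/156 | Detectable at 80%, 140/160 | Detectable at 80%, 132/156 |
|---|---|---|---|---|
| 10.7 | 68% | 66% | 3.5 | 3.5 |
| 16 | 37% | 35% | 5.2 | 5.3 |
| 18.6 | 29% | 28% | 6.0 | 6.2 |

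- Reconcile 80%, 360 and 300, and correct the completer split to match.
- Recompute the 84% moderation power in Figure 2 from the same SD. No inconsistency between 84% and 96% is claimed.
- State that a non-significant result will be read from the confidence interval against 3 points.

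The cost is rewording and rerunning the power simulation. Enrolment and endpoints do not change. The stated power is likely to look less favourable.

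### The 84% power for the literacy interaction does not follow from the assumptions it shares with the 96% main-effect power, and its 6-point scenario needs an unstated assumption

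*Protocol*

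**What the plan says.** All of this is in Protocol section 6.5.

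- **Main effect.** Success is defined thus: "the proposed intervention would be successful if it resulted in an increase of 3 points or more on this subscale". With 300 completers, "we would obtain 96% power to detect a clinically meaningful difference in the Bayley-III cognitive scores" (Figure 1). Allowing for unequal dropout, the sample "with complete follow-up will consist of approximately 130 control patients and 170 intervention patients".
- **Mechanism.** "The power was estimated based on a simulation study that assumed that the sole impact of the intervention was on increasing enrollment into EI". Enrolled children gain 10 points on average (SD 1 point) over those not enrolled, and the 3-point effect comes from an "increased rate of enrollment from 50% among controls to 80% among the intervention group".
- **Moderation.** Literacy, dichotomised on the SAHL, is the worked example for Aim 3. "We assume a rate of inadequate literacy of 50% in each group", and "the overall effect of the intervention on the cognitive score is the same as before". A simulation on these assumptions is said to show that "the proposed sample size would give us approximately 84% power to a 6-point difference in differences for the effect of the intervention" (Figure 2, n = 300).

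The section does not print the overall outcome SD, the alpha, the sidedness, the number of simulation runs, or enrolment by literacy group.

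**The concern.** The two power figures stand side by side, use the same 300 completers, and are presented as sharing their assumptions. A moderator that halves both arms doubles the standard error, and the interaction target (6 points) is double the main-effect target (3 points). The two powers should therefore agree closely, yet they differ by 12 percentage points.

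An overall effect of 3 with a 6-point gap between equal halves also leaves no freedom: one group gains 6 points and the other none. It is not obvious that the stated enrolment mechanism can produce this.

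The 84% is the only power figure offered for Aim 3. If it cannot be derived from the planning model, and applies only to a case where the navigator does nothing for half the families, it says little about which interactions the trial could detect.

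**Working it through.** **Inputs from section 6.5:** 130 control and 170 intervention completers; main effect 3 points; interaction 6 points; literacy 50/50 in each arm (65/65 and 85/85); benefit 10 points, SD 1; enrolment 50% and 80%. **Assumed, because not printed:** two-sided alpha 0.05, normal approximation.

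**1. Attempt to reproduce the printed figures.** Taking 1 point as the outcome SD gives power of essentially 100%. Using only the variance created by enrolment:
- control: 100 × 0.5 × 0.5 + 0.5 × 1 = 25.5 (SD 5.05)
- intervention: 100 × 0.8 × 0.2 + 0.8 × 1 = 16.8 (SD 4.10)
- SE = √(25.5/130 + 16.8/170) = 0.543; power 99.98% for 3 points, and 99.98% for the 6-point interaction if these variances hold in both literacy groups

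Neither 96% nor 84% follows from the printed inputs, so a further residual SD must have been used.

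**2. Ratio of standard errors at a common SD.**
- Main effect: SE = SD × √(1/130 + 1/170) = 0.1165 × SD
- Interaction: SE = SD × √(1/65 + 1/65 + 1/85 + 1/85) = 0.2330 × SD, exactly twice as large
- z is 3/(0.1165 × SD) for the main effect and 6/(0.2330 × SD) for the interaction, which are equal

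**3. Back-solving the SD.**
- For 96%: SD = 3/[(1.960 + 1.751) × 0.1165] = 6.94. Interaction power is then 96.0%.
- For 84%: SD = 3/[(1.960 + 0.994) × 0.1165] = 8.72. Main-effect power is then also 84%.
- At SD 6.94, the interaction with 84% power is (1.960 + 0.994) × 0.2330 × 6.94 = 4.8 points, not 6.

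The equality also holds for one-sided tests and for 150/150 or 180/180. With a one-sided main-effect test and a two-sided interaction test, interaction power is 92.4%. Keeping 0.05 for the main effect, an interaction alpha of 0.01 gives 87.2% and 0.005 gives 81.7%. Section 6.5 mentions no such alpha.

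**4. Subgroup effects and enrolment.** Let the effects be a and b, with (a + b)/2 = 3 and a − b = 6. Then a = 6 and b = 0. At 10 points per enrolled child, the enrolment gains are +60 and 0 percentage points. From 50% control enrolment in both groups, the first would reach 50 + 60 = 110%. Two routes avoid this.

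- *Control enrolment differs by literacy.* The first group must start at 40% or less. To keep 50% overall, the other must be at 60% or more.
- *EI benefit differs by literacy.* Enrolment rises from 50% to 80% in both groups, with a benefit of 20 points in one and 0 in the other: 0.3 × 20 = 6 and 0.3 × 0 = 0.

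**5. Power under each route.** Calibrating the residual SD so that the main effect has 96% power: the squared SE must be (3/3.711)² = 0.6536, enrolment contributes 0.2950, and (0.6536 − 0.2950)/0.013575 = 26.42, so the residual SD is 5.14.

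| Scenario | Interaction power |
|---|---|
| Control enrolment 40%/60%, benefit 10 in both | 96.7% |
| Control enrolment 20%/80%, benefit 10 in both | 97.5% |
| Control enrolment 0%/100%, benefit 10 in both | 99.5% |
| Enrolment 50% to 80% in both, benefit 20/0 | 87.2% |

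In the last row main-effect power falls. The arm variances become 75 + 0.5 + 26.42 = 101.92 and 96 + 0.8 + 26.42 = 123.22, so SE = √(101.92/130 + 123.22/170) = 1.228, z = 2.44 and power is about 69% (68% by simulation).

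**6. A smaller interaction.** As an illustration, enrolment gains of 40 and 20 points give effects of 4 and 2, an overall effect of 3 and an interaction of 2.

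| SD | Power for a 2-point interaction | Interaction with 80% power, 2.802 × 0.2330 × SD |
|---|---|---|
| 6.94 | 24% | 4.5 points |
| 8.72 | 17% | 5.7 points |

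**The case against.** The strongest reply is that the exact equality needs a single SD. In the protocol's enrolment model, variance depends on enrolment and benefit, so the two powers need not be identical. The 20-versus-0 benefit route keeps the effect acting only through enrolment, keeps the average benefit at 10 points, takes no rate above 80%, and gives about 87%. The figure is described as approximate and no run count is given. With 200 runs the Monte Carlo standard error near 87% is √(0.87 × 0.13/200) = 2.4 points, so 84% could be noise around it.

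Much of this stands. A reader might infer that the 6-point scenario is impossible because it needs 110% enrolment, or that 84% and 96% could never come from one model. The documents support neither inference, because unstated subgroup assumptions could produce the scenario and SD and alpha are not printed. But the 20/0 route does not rescue the text. It contradicts the stated benefit SD of 1 point, and the same model then gives about 69% for the main effect, not 96%. With the uniform 10-point benefit that is stated, interaction power is about 97% or more.

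It is also fair to reply that 84% is below 96%, that Aim 3 is worded as exploratory in Protocol section 2.2, that literacy is only an example, and that this figure does not set the sample size. These replies limit the severity. They do not make the figure derivable.

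**Conclusion.** The point holds in limited form. On the assumptions that section 6.5 says the two calculations share, the 6-point interaction should have about 96% power (about 97% or more under the enrolment model with a uniform benefit), not 84%. If 84% is right, the implied SD is 8.7 and the main effect also has 84%. The text does not show which figure is off. The scenario further rests on an unprinted difference by literacy, either in control enrolment (at most 40% versus at least 60%) or in EI benefit.

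This assumes a common residual SD and alpha, which the wording implies but does not print. The conflict is shown by the ratio of standard errors, not by rerunning the sponsor's simulation.

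A reader might infer that the 84% inflates the power for Aim 3. Relative to the 96% it does not. Its weakness is that it describes an extreme interaction, with no effect at all in half the families, and power for a 2-point interaction is only about 17% to 24% at the SDs implied by the plan's own figures. A reader might also go further and argue that both powers are too high because the true outcome SD is larger. That is a separate question about the missing SD; it applies equally to the 96% and is not settled here.

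Severity: minor to moderate.

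**What to change.** Recompute the Figure 2 power from the same residual SD, alpha, sidedness and enrolment model as the main effect, with enrolment by literacy and arm kept within 0 to 100% and the EI benefit by literacy stated. Print these inputs and the number of simulation runs, and replace or explain the 84%. If the recalculation points to an SD near 8.7, restate the 96% as well. Add the smallest interaction detectable with 80% power (about 4.5 points at SD 6.9, or 5.7 at SD 8.7), so that a non-significant interaction can be read against it.

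The cost is one rerun of the simulation, a revised paragraph and a small table in section 6.5. No design change and no additional participants are needed.
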